#### 3.2 Secondary Objective(s) & Hypothesis (es)

1. **Objective:** To estimate progression-free survival (PFS), overall survival (OS), the locoregional control rate (LRC), and distant metastases (DM) rate at 1- and 2-years in subjects treated with pembrolizumab given in combination with CRT.

**Hypothesis**: The addition of pembrolizumab to standard CRT will show increased efficacy in terms of key survival endpoints utilized in head and neck cancer.

2. **Objective:** To determine the best overall response rate (ORR) as defined by RECIST 1.1 at treatment end imaging in subjects with Stage III-IVB SCCHN treated with pembrolizumab given in combination with CRT.

**Hypothesis**: The addition of pembrolizumab to standard CRT will show superior ORR compared to historical controls.

4. **Objective:** To estimate the quality of life (QOL) of subjects with Stage III-IVB SCCHN treated with pembrolizumab in combination with CRT during therapy, treatment end, and 1- and 2-years following treatment.

**Hypothesis**: Acute and long-term QOL of participants treated with the combination of pembrolizumab and low dose weekly cisplatin and radiation will be superior to historical controls.

5. **Objective:** To correlate ORR, PFS, OS, LRC, and DM with tumor PD-L1 expression in subjects with Stage III-IVB SCCHN treated with pembrolizumab in combination with CRT.

**Hypothesis**: High PD-L1 expression has correlated with responses in the metastatic setting and will correlate with key disease response and survival outcomes in the curative intent setting.

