## 4.2.3.5 **Preliminary Results and Rationale for Expansion Cohort**

The current study has enrolled 27 patients from November 18, 2015 to August 6, 2016. The study is currently on hold for an interim safety and efficacy analysis. As of the data lock on September 14, 2016, 20 (74.1%) patients with HPV positive (p16 positive) disease and 7 (15.9%) with HPV negative (p16 negative) disease have enrolled. Early response data in imaged patients (n=9), shows a CR (CT and/or PET or pathologic CR on salvage surgery) in 8/8 (100%) of HPV positive patients and a PR in the single HPV negative patient. We anticipate easily hitting our primary endpoint of CR rate >60% in our HPV positive population based on these early results. However, based on our lack of HPV negative patients, it is unclear what responses will be seen.

Recent data analysis of an internal study (NCT01386632) using standard of care high-dose cisplatin (100 mg/m2 on days 1, 22, and 43) in a similar cohort of patients was performed. Distinct differences in response were seen in the HPV+ and HPV- groups, which mirror efficacy findings in similar studies. This analysis has revealed that 20 of 27 (74%) of evaluable patients with HPV positive disease achieved a CR (based on 3-month post-radiation CT and/or PET or subsequent salvage surgery). In the same study, the evaluable patients in the HPV negative cohort had 6 of 12 (50%) achieving the same CR endpoint.

Due to the historically good responses in HPV positive disease and the early findings in our current HPV positive cohort, we propose evaluation of efficacy separately in the HPV positive and HPV negative cohorts. As a result, we propose adding expansion cohorts after the interim analysis to explore efficacy in each of these unique populations. Addition of both HPV negative and HPV positive patients will provide further insight into efficacy of this novel combination.

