#### 8.4.7.4 Subgroup Analyses and Effect of Baseline Factors

All efficacy endpoints CR rate, ORR, PFS, OS, LRC rate, and DM rate will be evaluated and compared based on:

- HPV-positive and HPV-negative status
- PD-L1 positive and PD-L1 negative status
- Additional correlative studies as pertinent
- ECOG PS 0 or 1
- Key demographic variables (i.e. age, sex, etc.) as deemed appropriate

Differences in subgroups will be evaluated using appropriate statistical techniques adjusting for key demographic variables. Models will include logistic regression and proportional hazards regression.

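### The PD-L1 and other marker comparisons pool both HPV cohorts and name only demographic variables for adjustment, so an HPV difference in outcome can bias the marker association in either direction

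*Combined protocol and SAP*

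**What the plan says.** Secondary objective 5 (section 3.2) is "To correlate ORR, PFS, OS, LRC, and DM with tumor PD-L1 expression in subjects with Stage III-IVB SCCHN", with the hypothesis that high expression goes with better response and survival. It is stated for all subjects together. Section 3.3 adds exploratory correlations of tumour and blood profiles with efficacy, also without a split by HPV.

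Section 8.4.7.4 sets out how the comparisons are made. All efficacy endpoints, CR included, are compared by a list of factors. Among them are "HPV-positive and HPV-negative status", "PD-L1 positive and PD-L1 negative status", "Additional correlative studies as pertinent" and, as a separate item, "Key demographic variables (i.e. age, sex, etc.) as deemed appropriate". On method it says "Differences in subgroups will be evaluated using appropriate statistical techniques adjusting for key demographic variables" and "Models will include logistic regression and proportional hazards regression". It mentions no HPV term, stratum or interaction for the marker models.

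Elsewhere the plan treats HPV status as closely related to response. Section 4.2.3.5 reports from an internal study of high-dose cisplatin that "Distinct differences in response were seen in the HPV+ and HPV- groups, which mirror efficacy findings in similar studies". On that basis the trial was split into cohorts of 34 HPV-positive and 23 HPV-negative subjects, each with its own null and target CR rate (section 8.4.7.3).

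**The concern.** A pooled comparison of PD-L1-positive with PD-L1-negative subjects also compares two groups that may hold different shares of HPV-positive patients. If they do, part or all of any outcome difference between them is an HPV difference. The variables named for adjustment, age and sex, are not HPV status, and HPV status sits in a different item of the same list.

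The same applies to every other marker whose frequency differs between HPV-positive and HPV-negative tumours. One marker named in section 4.2.3.3, the immune response specific to HPV, is tied to HPV status by its nature.

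At stake is the reading of objective 5. An association in the hypothesised direction could appear with no PD-L1 effect in either cohort, or a real effect could be hidden if the imbalance runs the other way. Section 4.2.3.2 intends these results to inform later biomarker work.

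**Working it through.** **Inputs from the documents**
- Cohort sizes: 34 HPV-positive, 23 HPV-negative (section 2.1).
- Reference CR rates: 20/27 = 0.741 and 6/12 = 0.500, which reproduce the stated 74% and 50% (section 8.4.7.3).
- Hypothesised CR rates: 90% and 75% (section 3.1).

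**Strength of the HPV–CR relation in these figures**
- Targets: (0.90/0.10)/(0.75/0.25) = 9/3 = 3.00.
- Reference rates: (0.74/0.26)/(0.50/0.50) = 2.85.

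**Assumptions**
- PD-L1 has no effect within either cohort.
- PD-L1-positive prevalence is *a* in HPV-positive and *b* in HPV-negative subjects. The documents do not give *a* or *b*, so a range is shown.
- There is no demographic adjustment.

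**Formula.** With CR rates *p1* (HPV-positive) and *p2* (HPV-negative):
- CR in PD-L1-positive = (34·a·p1 + 23·b·p2)/(34·a + 23·b).
- CR in PD-L1-negative is the same with 1−a and 1−b.

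**Worked case: a = 0.80, b = 0.30, CR 90%/75%**
- PD-L1-positive: 27.2 + 6.9 = 34.1 subjects. CRs: 27.2×0.90 + 6.9×0.75 = 29.655, or 87.0%.
- PD-L1-negative: 6.8 + 16.1 = 22.9 subjects. CRs: 6.8×0.90 + 16.1×0.75 = 18.195, or 79.5%.
- Crude odds ratio: (29.655/4.445)/(18.195/4.705) = 1.73.

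At CR 74%/50% the same prevalences give 69.1% versus 57.1%, odds ratio 1.68.

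**Range.** The rejection columns come from simulated trials of 34 + 23 subjects, using a two-sided 5% test of two proportions that ignores HPV.

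| PD-L1+ prevalence, HPV+ / HPV− | Odds ratio at 90/75 | Odds ratio at 74/50 | Rejects at 90/75 | Rejects at 74/50 |
|---|---|---|---|---|
| 50% / 50% | 1.00 | 1.00 | 5.1% | 5.1% |
| 60% / 40% | 1.24 | 1.22 | 6.3% | 6.6% |
| 70% / 40% | 1.39 | 1.36 | about 8% | about 9% |
| 80% / 30% | 1.73 | 1.68 | about 13% | about 16% |
| 30% / 70% (reversed) | 0.65 | 0.67 | not run | not run |

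A Mantel-Haenszel test stratified by HPV stays near 5% (4.2% to 5.0% in the scenarios tabulated for it). The stratified odds ratio is 1.00 by construction.

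**Room for covariates.** Expected subjects without a CR at the target rates: 34×0.10 + 23×0.25 = 3.40 + 5.75 = 9.15. About three of the nine are HPV-positive. At the reference rates the number is 34×0.26 + 23×0.50 = 20.3. Either way a logistic model can carry few terms.

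**The case against.** Several objections have force.

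- **Prevalence is unknown.** The documents give no PD-L1 frequency by HPV status, so neither the size nor the direction of the bias can be stated. A reader might infer that PD-L1 is known to be imbalanced and that the bias is certain; nothing in the documents supports that. At equal prevalence there is none.
- **The simulated test is not the planned one.** The plan adjusts for demographics, and if age or sex tracks HPV status, part of the bias goes. The documents do not show how much. The choice of test also matters: an unadjusted logistic Wald test at 90/75 rejects 5.2% of the time at 70%/40% and 9.3% at 80%/30%, against 2.4% at equal prevalence. The inflation remains, at lower absolute levels.
- **No confirmatory claim is planned.** Section 8.4.3.1 limits secondary endpoints to confidence intervals, and section 4.2.3.4 calls the molecular work retrospective and exploratory. A reader might infer that the plan will falsely confirm the PD-L1 hypothesis. That goes too far, although section 8.4.7.4 does say subgroups are compared with regression models.
- **The illustration uses CR.** Objective 5 lists ORR, PFS, OS, LRC and DM. CR is covered by section 8.4.7.4, but the documents give no HPV-specific rates for the other five, so nothing is quantified for them.
- **The HPV difference is estimated from few patients.** For 20/27 versus 6/12, Fisher's two-sided p is 0.16. The sponsor nevertheless built separate cohorts and targets on it.
- **The wording is open.** The reference to suitable techniques and the open-ended demographic list leave room for HPV adjustment, so it would be wrong to say that the plan rules it out. But the one adjustment set it names omits HPV. The separate evaluation by HPV in section 4.2.3.5 concerns efficacy and is not carried into the marker analyses.

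**Conclusion.** The point stands as a gap in the specified adjustment. Following section 8.4.7.4 as worded can give a PD-L1 or other marker association confounded by HPV status, a factor on which the plan itself bases its cohorts and targets. The bias arises only if marker frequency differs by HPV status, and it can run either way.

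For CR, under the assumptions above, the crude odds ratio with no true PD-L1 effect lies between 1.00 and about 1.7 for prevalence gaps from none to 80% versus 30%, and falls below 1 if the gap is reversed. These figures illustrate the mechanism; they do not predict this trial's error rate. The practical consequence is a possibly biased, hypothesis-generating association. The primary CR analysis is not affected.

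**What to change.** In section 8.4.7.4, state that HPV (p16) status enters every PD-L1 and correlative-marker model as a stratum or covariate, with priority over age, sex and other demographic terms because few non-responders are expected. Specifically:

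- For CR, ORR and the LRC and DM rates as analysed in Table 7: Mantel-Haenszel or exact methods stratified by HPV, or logistic regression with an HPV term.
- For PFS and OS: Cox models stratified by HPV.
- Within-cohort marker results: descriptive only. With about nine subjects without a CR expected at the target rates, cohort-specific estimates would be too imprecise to interpret singly.

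The cost is a change of wording. Known p16 status is an entry requirement (section 5.1.2, with HPV DNA testing where p16 is indeterminate), and PD-L1 is characterised retrospectively (section 7.1.2.7.1), so no new data are needed. The statistical price is a somewhat wider interval for the marker effect, and fewer demographic covariates in the same model.

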# 9.0 LABELING, PACKAGING, STORAGE AND RETURN OF CLINICAL SUPPLIES

#### 9.1 **Investigational Product**

The investigator shall take responsibility for and shall take all steps to maintain appropriate records and ensure appropriate supply, storage, handling, distribution and usage of investigational product in accordance with the protocol and any applicable laws and regulations.

Clinical Supplies are as summarized in Table 8.

Table 8 Product Descriptions

Product Name & Potency	Dosage Form
Pembrolizumab 100 mg/ 4mL 	Solution for Injection

1-Provided by Merck

#### 9.2 **Packaging and Labeling Information**

Clinical supplies will be affixed with a clinical label in accordance with regulatory requirements.

#### 9.3 Clinical Supplies Disclosure

The Pembrolizumab product that will be supplied for this trial is not an approved US commercial product at this time. It is, however, filed to the Merck IND along with data supporting a claim of analytical comparability of this product to all other pembrolizumab products being used in the clinic, some of which have been approved by the US FDA for commercial use.

This trial is open-label; therefore, the subject, the trial site personnel, Sanford Research and/or designee are not blinded to treatment. Drug identity (name, strength) is included in the label text.

#### 9.4 Storage and Handling Requirements

Clinical supplies must be stored in a secure, limited-access location under the storage conditions specified on the label.

Receipt and dispensing of trial medication must be recorded by an authorized person at the trial site.

Clinical supplies may not be used for any purpose other than that stated in the protocol.

#### 9.5 **Returns and Reconciliation**

The investigator is responsible for keeping accurate records of the clinical supplies received from Merck or designee, the amount dispensed to and returned by the subjects and the amount remaining at the conclusion of the trial.

Upon completion or termination of the study, all unused and/or partially used investigational product will be destroyed at the site per institutional policy. It is the Investigator's responsibility to arrange for disposal of all empty containers, provided that procedures for proper disposal have been established according to applicable federal, state, local and institutional guidelines and procedures, and provided that appropriate records of disposal are kept.

#### **10.0 ADMINISTRATIVE AND REGULATORY DETAILS**

#### 10.1 Confidentiality

#### 10.1.1 **Confidentiality of Data**

By signing this protocol, the investigator affirms to Sanford Research that information furnished to the investigator by Sanford Research will be maintained in confidence, and such information will be divulged to the institutional review board, ethics review committee (IRB/ERC) or similar or expert committee; affiliated institution and employees, only under an appropriate understanding of confidentiality with such board or committee, affiliated institution and employees. Data generated by this trial will be considered confidential by the investigator, except to the extent that it is included in a publication as provided in the Publications section of this protocol.

#### 10.1.2 Confidentiality of Subject Records

By signing this protocol, the investigator agrees that Sanford Research (or Sanford Research representative), IRB/ERC, or regulatory authority representatives may consult and/or copy trial documents in order to verify worksheet/case report form data. By signing the consent form, the subject agrees to this process. If trial documents will be photocopied during the process of verifying worksheet/case report form information, the subject will be identified by unique code only; full names/initials will be masked prior to transmission to Sanford Research. See the procedure manual for additional information.

By signing this protocol, the investigator agrees to treat all subject data used and disclosed in connection with this trial in accordance with all applicable privacy laws, rules and regulations.

#### 10.1.3 Confidentiality of Investigator Information

By signing this protocol, the investigator recognizes that certain personal identifying information with respect to the investigator, and all sub-investigators and trial site personnel,

may be used and disclosed for trial management purposes, as part of a regulatory submissions, and as required by law. This information may include:

- 1. name, address, telephone number and e-mail address;
- 2. hospital or clinic address and telephone number;
- 3. curriculum vitae or other summary of qualifications and credentials; and
- 4. other professional documentation.

Consistent with the purposes described above, this information may be transmitted to Sanford Research, and subsidiaries, affiliates and agents of Sanford Research and Merck.

Additionally, the investigator's name and business contact information may be included when reporting certain serious adverse events to regulatory authorities or to other investigators. By signing this protocol, the investigator expressly consents to these uses and disclosures.

As this is a multicenter trial, in order to facilitate contact between investigators, Sanford Research may share an investigator's name and contact information with other participating investigators upon request.

#### 10.1.4 Confidentiality of IRB/IEC Information

Sanford Research is required to record the name and address of each IRB/IEC member that reviews and approves this trial. Sanford Research is also required to document that each IRB/IEC meets regulatory and ICH GCP requirements by requesting and maintaining records of the names and qualifications of the IRB/IEC members and to make these records available for regulatory agency review upon request by those agencies.

#### 10.2 Compliance with Financial Disclosure Requirements

Financial Disclosure requirements are outlined in the US Food and Drug Administration Regulations, Financial Disclosure by Clinical Investigators (21 CFR Part 54). It is Sanford Research's responsibility to determine, based on these regulations, whether a request for Financial Disclosure information is required. It is the investigator's/sub investigator's responsibility to comply with any such request.

The investigator/sub investigator(s) agree, if requested by Sanford Research in accordance with 21CFR Part 54, to provide his/her financial interests in and/or arrangements with Sanford Research to allow for the submission of complete and accurate certification and disclosure statements. The investigator/sub investigator(s) further agree to provide this information on a Certification/Disclosure Form, commonly known as a financial disclosure form, provided by Sanford Research or through a secure password-protected electronic portal provided by Sanford Research. The investigator/subinvestigator(s) also consent to the transmission of this information to Sanford Research for these purposes.

#### 10.3 Compliance with Law, Audit and Debarment

By signing this protocol, the investigator agrees to conduct the trial in an efficient and diligent manner and in conformance with this protocol; generally accepted standards of Good Clinical Practice (e.g., International Conference on Harmonization of Technical Requirements for Registration of Pharmaceuticals for Human Use Good Clinical Practice: Consolidated Guideline and other generally accepted standards of good clinical practice); and all applicable federal, state and local laws, rules and regulations relating to the conduct of the clinical trial.

The investigator also agrees to allow monitoring, audits, IRB/ERC review and regulatory authority inspection of trial-related documents and procedures and provide for direct access to all trial-related source data and documents.

The investigator agrees not to seek reimbursement from subjects, their insurance providers or from government programs for procedures included as part of the trial reimbursed to the investigator by Sanford Research.

The investigator shall prepare and maintain complete and accurate trial documentation in compliance with Good Clinical Practice standards and applicable federal, state and local laws, rules and regulations; and, for each subject participating in the trial, provide all data, and, upon completion or termination of the clinical trial, submit any other reports to Sanford Research as required by this protocol or as otherwise required pursuant to any agreement with Sanford Research.

Trial documentation will be promptly and fully disclosed to Sanford Research by the investigator upon request and also shall be made available at the trial site upon request for inspection, copying, review and audit at reasonable times by representatives of Sanford Research or any regulatory authorities. The investigator agrees to promptly take any reasonable steps that are requested by Sanford Research as a result of an audit to cure deficiencies in the trial documentation and worksheets/case report forms.

The investigator must maintain copies of all documentation and records relating to the conduct of the trial in compliance with all applicable legal and regulatory requirements. This documentation includes, but is not limited to, the protocol, worksheets/case report forms, advertising for subject participation, adverse event reports, subject source data, correspondence with regulatory authorities and IRBs/ERCs, consent forms, investigator's curricula vitae, monitor visit logs, laboratory reference ranges, laboratory certification or quality control procedures and laboratory director curriculum vitae. By signing this protocol, the investigator agrees that documentation in an ICH region or until there are no pending or contemplated marketing applications in an ICH region or until at least 2 years have elapsed since the formal discontinuation of clinical development of the investigational product.

Because the clinical development and marketing application process is variable, it is anticipated that the retention period can be up to 15 years or longer after protocol database lock. Sanford Research will determine the minimum retention period and notify the investigator when documents may be destroyed Sanford Research also recognizes that documents may need to be retained for a longer period if required by local regulatory requirements. All trial documents shall be made available if required by relevant regulatory authorities. The investigator must consult with and obtain written approval by Sanford Research prior to destroying trial and/or subject files. ICH Good Clinical Practice guidelines recommend that the investigator inform the subject's primary physician about the subject's participation in the trial if the subject has a primary physician and if the subject agrees to the primary physician being informed.

The investigator will promptly inform Sanford Research of any regulatory authority inspection conducted for this trial.

Persons debarred from conducting or working on clinical trials by any court or regulatory authority will not be allowed to conduct or work on Sanford Research's trials. The investigator will immediately disclose in writing to Sanford Research if any person who is involved in conducting the trial is debarred or if any proceeding for debarment is pending or, to the best of the investigator's knowledge, threatened.

In the event Sanford Research prematurely terminates a particular trial site, Sanford Research will promptly notify that trial site's IRB/IEC.

